8.5 Medical Monitoring

It is the responsibility of the Principal Investigator to oversee the safety of the study at his/her site. This safety monitoring will include careful assessment and appropriate reporting of adverse events as noted above, as well as the construction and implementation of a site data and safety-monitoring plan (see section 10 "Study Monitoring, Auditing, and Inspecting"). Medical monitoring will include a regular assessment of the number and type of serious adverse events.

The occurrence of adverse events will be sought by non-directive questioning of the patient at each visit during the study. Adverse events also may be detected when the patient volunteers them during or between visits or through physical examination, laboratory test, or other assessments. Please see Supplemental 3 for a detailed description of safety monitoring. Clinically significant abnormal laboratory values or test results will be identified through a review of values outside of normal ranges/clinically notable ranges, significant changes from baseline or the previous visit, or values which are non-typical in patient with underlying disease. Investigators have the responsibility for managing the safety of individual patient and identifying adverse events. Alert ranges for labs and other test abnormalities are included determined by the Mayo Clinic Arizona and Mayo Medical Laboratory. Adverse events will be recorded in the Adverse Events Case Report Form (CRF) under the signs, symptoms or diagnosis associated with them, and severity. All adverse events will be treated appropriately. Once an adverse event is detected, it should be followed until its resolution or until it is judged to be permanent, and assessment should be made at each visit (or more frequently, if necessary) of any changes in severity, the suspected relationship to the study drug, the interventions required to treat it, and the outcome (see Supplemental 3). Information about common side effects already known about the investigational drug can be found in the package insert. This information will be included in the patient informed consent and should be discussed with the patient during the study as needed. The investigator will also instruct each patient to report any new adverse event (beyond the protocol observation period) that the patient, or the patient's personal physician, believes might reasonably be related to study treatment. This information should be recorded in the investigator's source documents, however, if the AE meets the criteria of an SAE. To ensure patient safety, every SAE (see Supplemental 3 for definition), regardless of suspected causality, occurring after the patient has provided informed consent and after the patient begins taking study drug and until 30 days after the patient has stopped study participation will be recorded and reported to Incyte. Any SAEs experienced after this 30-day period should only be reported to Incyte if the investigator suspects a causal relationship to the study drug. All malignant neoplasms will be assessed as serious under "medically significant" if other seriousness criteria are not met. Medical and scientific judgment will be exercised in deciding whether other situations should be considered serious reactions, such as important medical events that might not be immediately life threatening or result in death or hospitalization but might jeopardize the patient or might require intervention to prevent one of the outcomes listed in SAE. Any suspected transmission via a medicinal product of an infectious agent is also considered a serious adverse reaction. All AEs (serious and non-serious) are captured and recorded, SAEs also require individual reporting (see Supplemental 3). To ensure patient safety, each pregnancy occurring while the patient is on study treatment must be reported to the sponsor-investigator within 24 hours of learning of its occurrence. The pregnancy should be followed up to determine outcome, including spontaneous or voluntary termination, details of the birth, and the presence or absence of any birth defects, congenital abnormalities, or maternal and/or newborn complications. Pregnancy follow-up should be recorded on the same form and should include an assessment of the possible relationship to the study treatment. Any SAE experienced during the pregnancy and unrelated to the pregnancy must be reported on a SAE form.

9 Data Handling and Record Keeping

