For this study, the study treatment follow-up period is defined as 30 days following the last administration of study treatment.

Preexisting Condition

A preexisting condition is one that is present at the start of the study. A preexisting condition should be recorded as an adverse event if the frequency, intensity, or the character of the condition worsens during the study period.

General Physical Examination Findings

At screening, any clinically significant abnormality should be recorded as a preexisting condition. At the end of the study, any new clinically significant findings/abnormalities that meet the definition of an adverse event must also be recorded and documented as an adverse event.

A thorough baseline screening will be followed for all subjects and is outlined in Table-2. A detailed list of the methods in which baseline screening will be performed is outlined in Supplemental 2. All blood draws and safety assessments must be performed **prior** to study treatment administration. Appropriate safety assessments (e.g., evaluation of AEs and SAEs) should be repeated after dosing with study treatment. A physical examination, including general appearance and vital signs, will be performed as indicated in Table-2. If indicated, based on medical history and/or symptoms, additional exams will be performed at the discretion of the investigator. If possible, the same member of the study site staff throughout the study will perform assessments for an individual subject. Information for all physical examinations will be included in the source documentation at the study site. Significant findings that are present prior to the subject signing informed consent will be included in the Medical History. Significant findings made after the signing of the informed consent, which meet the definition of an AE, must be recorded as an AE. Vital signs (blood pressure, pulse, height, weight) will be assessed at each physical examination as indicated in Table-2 (see Supplemental 2 for details on how to acquire vital signs). Whether action needs to be taken to address notable vital signs will be decided by the investigator, considering the overall status of the subject.

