8.2 Recording of Adverse Events

At each contact with the subject, the study team must seek information on adverse events by specific questioning and, as appropriate, by examination. Information on all adverse events should be recorded immediately in the source document, and also in the appropriate adverse event section of the case report form (CRF). All clearly related signs, symptoms, and abnormal diagnostic, laboratory or procedure results should recorded in the source document.

All adverse events occurring during the study period must be recorded. The clinical course of each event should be followed until resolution, stabilization, or until it has been ultimately determined that the study treatment or participation is not the probable cause. Serious adverse events that are still ongoing at the end of the study period must be followed up, to determine the final outcome. Any serious adverse event that occurs during the Adverse Event Reporting Period and is considered to be at least possibly related to the study treatment or study participation should be recorded and reported immediately.

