To ensure patient safety, every SAE, regardless of causality, occurring after the patient has provided informed consent and until 30-days after the subject stopped study participation must be reported to Bristol Myers Squibb and Company SAEs, whether related or not related to study drug, and pregnancies must be reported to BMS within 24 hours \ 1 Business Day of becoming aware of the event. SAEs must be recorded on either CIOMS, MedWatch, or approved study specifi/institutional SAE form. Any SAEs experienced after the 30-days period should only be reported to Bristol Myers Squibb and Company and the Mayo Clinic IRB if the investigator suspects a causal relationship to study treatment. Recurrent episodes, complications, or progression of the initial SAE must be reported as follow-up to the original episode, regardless of when the event occurs. This report must be submitted as soon as possible but no later than 5 days from the investigator receiving the follow-up information. SAE should be followed up until resolution or until it is judged to be permanent. An SAE that is considered completely unrelated to a previously reported one should be reported separately as a new event.

BMS Reporting:	
SAE Email Address:	
SAE Facsimile Numb	er:

If only limited information is initially available, follow-up reports are required. (Note: Follow-up SAE reports should include the same investigator term(s) initially reported.)

If an ongoing SAE changes in its intensity or relationship to study drug or if new information becomes available, a follow-up SAE report should be sent within 24 hours \ 1 Business Day to BMS using the same procedure used for transmitting the initial SAE report.

All SAEs should be followed to resolution or stabilization.

Information collected on the adverse event worksheet (and entered in the research database):

- Subject's name:
- Medical record number:
- Disease/histology (if applicable):
- The date the adverse event occurred:
- Description of the adverse event:
- Relationship of the adverse event to the research (drug, procedure, or intervention*):
- If the adverse event was expected:
- The severity of the adverse event: (use a table to define severity scale 1-5**)
- If any intervention was necessary:
- Resolution: (was the incident resolved spontaneously, or after discontinuing treatment)
- Date of Resolution:

AE Reporting:

Its relationship to the:

- Study treatment (no/yes), or
- Investigational treatment (no/yes), or

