All Serious Adverse Events ("SAE") required to be reported pursuant to the Protocol shall be provided to Bristol Myers Squibb and Company and its representatives by Institution or Principal Investigator within twenty-four (24) hours of learning of the event as well as provide any additional reports agreed upon by the Institution or Principal Investigator and Bristol Myers Squibb and Company's contact below. SAE Reports will be sent to the email address provided below. By sending to this e-mail address, the Bristol Myers Squibb and Company Pharmacovigilance group and the Bristol Myers Squibb and Company clinical operations project manager will receive copies of the reports. This process will be tested and established before the first patient is enrolled in the trial. Notwithstanding anything to the contrary herein, Institution or Principal Investigator will have the primary responsibility of reporting adverse events ("AE") to regulatory authorities.

Copies of IND safety reports submitted to the FDA by the Institution will be shared with the contact below so that these reports can be evaluated and included in investigator brochure or Incyte IND safety submissions as required to ensure safety of other patients who are receiving the product from Bristol Myers Squibb and Company for sponsored trials.

If, following initiation of the investigational product, it is subsequently discovered that a study participant is pregnant or may have been pregnant at the time of investigational product exposure, including during at least 5 half-lives after product administration, the investigational product will be permanently discontinued in an appropriate manner (eg, dose tapering if necessary for participant).

The Sponsor-Investigator must immediately notify of this event and complete one of the following forms within 24 hours of awareness of the event via either the CIOMS, MedWatch or appropriate Pregnancy Surveillance Form in accordance with SAE reporting procedures.

Protocol-required procedures for study discontinuation and follow-up must be performed on the participant. Follow-up information regarding the course of the pregnancy, including perinatal and neonatal outcome and, where applicable, offspring information must be reported on the CIOMS, MedWatch, BMS Pregnancy

Surveillance Form, or approved site SAE form. A BMS Pregnancy Surveillance Form may be provided upon request.

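### Section 8.5 sends SAEs to Incyte, a company with no stated role in the trial, and starts reporting only once study drug has begun, against Bristol Myers Squibb and informed consent in Section 8.3

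*Combined protocol and SAP*

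**What the plan says.** **Section 8.5, Medical Monitoring.** This section states an SAE rule of its own. It covers events irrespective of suspected cause, but only those "occurring after the patient has provided informed consent and after the patient begins taking study drug". Up to 30 days after participation ends, these SAEs "will be recorded and reported to Incyte". SAEs after that period also go to Incyte, if the investigator suspects a causal link.

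**Section 8.3.1, SAE Reporting.** The rule covers "every SAE, regardless of causality, occurring after the patient has provided informed consent and until 30-days after the subject stopped study participation". The recipient is Bristol Myers Squibb. The time allowed is 24 hours, with one business day written beside it as an alternative. Later SAEs with suspected causality go to Bristol Myers Squibb and the Mayo IRB. Reports on recurrence, complications or progression are due "no later than 5 days from the investigator receiving the follow-up information". A later paragraph sets 24 hours or one business day when intensity or relationship changes or new information arrives.

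**Section 8.3.2, SAE Reporting to the Sponsor.** All SAEs reportable under the protocol go to Bristol Myers Squibb within 24 hours, with no business-day alternative. Copies of IND safety reports are shared for use in the "investigator brochure or Incyte IND safety submissions".

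**Section 8.2.** An SAE within the Adverse Event Reporting Period that "is considered to be at least possibly related to the study treatment or study participation should be recorded and reported immediately". No recipient is named.

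**Section 8.1.** Under the heading for the Adverse Event Reporting Period, the follow-up period is "30 days following the last administration of study treatment".

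**Roles.** Section 12.1 names Bristol Myers Squibb as funder and Section 5.3 as drug supplier. Incyte appears only in 8.5 and in the IND-copies sentence of 8.3.2.

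**The concern.** These are operative instructions to site staff, not background. Two Mayo sites take part (Arizona and Florida, per the Study Summary), and different staff may work from different sections. Someone who turns to Medical Monitoring for the SAE rule finds what reads as a complete one, with a recipient and a window, and a pointer to Supplemental 3 rather than to 8.3.1.

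Two consequences follow from applying 8.5 as written. The report goes to a company that neither funds the study nor supplies the drug, and the company that should assess it does not receive it in time. An SAE between consent and first dose, for example during withdrawal of the treatments listed in Table 1, is not reported at all, although 8.3.1 requires it.

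What is at stake is prompt and complete safety reporting. Sections 8.2 and 8.5 both require all adverse events to be recorded, so the point does not show that events would be lost from the trial database.

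**Working it through.** No sample-size or power figure is involved. The check is a comparison of sections plus calendar arithmetic from the protocol's own schedule.

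| Element | 8.1 / 8.2 | 8.3.1 | 8.3.2 | 8.5 |
|---|---|---|---|---|
| Recipient | none named | Bristol Myers Squibb | Bristol Myers Squibb | Incyte |
| Start | not stated for SAEs | informed consent | not stated | consent and study drug begun |
| Causality | immediate rule stated for possibly related SAEs | any | any SAE the protocol makes reportable | any |
| End | 30 days after last dose | 30 days after participation stops | not stated | 30 days after participation stops |
| Initial deadline | immediately | 24 hours or one business day | 24 hours | not stated |

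Sections 8.3.1 and 8.5 conflict on recipient and start. They agree on causality and end date; on those two elements the mismatch is with 8.2 and 8.1.

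**Start.** Section 3.3 gives screening/washout as 1 to 4 weeks. Section 4.1 requires consent before any study activity. Assuming consent when screening opens:
- shortest gap: 1 × 7 = 7 days
- longest gap: 4 × 7 = 28 days

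SAEs in that interval are reportable under 8.3.1 and not under 8.5.

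**End.** Dosing stops at week 24 (Section 5.2) and the last evaluation is at week 28 (Section 3.1). For a completer, ignoring the ±3-day visit window:
- last dose: 24 × 7 = day 168; plus 30 = day 198 (8.1)
- participation ends: 28 × 7 = day 196; plus 30 = day 226 (8.3.1 and 8.5)
- difference: 226 − 198 = 28 days

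**Initial deadline.** For an SAE learned of on a Friday afternoon, 24 hours ends on Saturday. One business day can run to Monday, about 72 hours if there is no holiday. Section 8.3.1 permits either; 8.3.2 permits only the first.

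**Follow-up deadline.** 5 days = 5 × 24 = 120 hours, against 24 hours (120 / 24 = 5) or, over a weekend, about 72 hours (120 / 72 ≈ 1.7). The triggers are worded differently, but a complication or progression is normally also new information, so one event can meet both.

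**The case against.** The best defence is that the correct route is already in the protocol. Section 8.3.2 directs every SAE reportable under the protocol to Bristol Myers Squibb, says the e-mail process is tested before the first patient is enrolled, and sets up a reconciliation in which missed cases are sent to Bristol Myers Squibb at once. Section 8.5 opens by relying on reporting as already described. Incyte then looks like a leftover name from another protocol, and no Incyte reporting channel is visible (contact details were removed from the public text). Much of this stands, and it lowers the risk. It does not cure the text: 8.5 goes on to state a different rule, no sentence says that 8.3.1 prevails over it, and reconciliation recovers a case only after the deadline.

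Four stronger readings are tempting, and the documents do not support them:

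- *Section 8.3.2 also makes Incyte an SAE recipient.* It does not. The name appears only in describing how copies of IND safety reports may be used.
- *Section 8.2 excuses unrelated SAEs from reporting.* It sets an immediate rule for possibly related ones and is silent on the rest. Staff can comply with 8.2 and 8.3.1 together.
- *The 28-day difference in end dates means lost reports.* Working to the later date satisfies both rules, and 8.3.1 and 8.5 already share it.
- *The two follow-up deadlines flatly contradict each other.* They have different stated triggers; the fault is that the triggers overlap.

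A reader might also ask for an extra contact at day 30 after last dose. That would match only the 8.1 period, not the 8.3.1 window, which for a completer closes about day 58 after last dose (226 − 168).

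**Conclusion.** The point holds for Section 8.5. As written it names the wrong recipient by the protocol's own account of who funds and supplies the trial, and it starts later than 8.3.1 by the whole screening/washout period, about 7 to 28 days per subject. That range assumes consent at the start of screening. The end-date difference of 28 days for completers, the business-day alternative, the overlapping follow-up triggers and the narrower wording of 8.2 are secondary: they need tidying, but none by itself obliges staff to miss a report.

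That Incyte is carried-over text is an inference. The documents show only that it has no stated role. They give no SAE rate, so the number of reports affected cannot be estimated. They also do not show that any report has gone astray.

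**What to change.** 1. In 8.5, replace Incyte with Bristol Myers Squibb in both places, and correct the stray name in the IND-copies sentence of 8.3.2.
2. In 8.5, delete the condition that study drug has begun. Better still, replace the whole 8.5 SAE rule with a cross-reference to 8.3.1, so that the rule is stated once.
3. Reconcile 8.1, 8.2, 8.3.1 and 8.3.2 to one end date and one initial deadline, and decide whether the business-day alternative stays.
4. In 8.3.1, give one follow-up deadline per trigger, with triggers that do not overlap.
5. In 8.2, say that its immediate rule does not narrow the duty in 8.3.1 to report SAEs whatever their cause.

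The sponsor-investigator and Bristol Myers Squibb should agree the end date and deadlines. The cost is a wording amendment and a note to both sites, with no new visits, data or analyses.

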9.1 Confidentiality

Information about study subjects will be kept confidential and managed according to the requirements of the Health Insurance Portability and Accountability Act of 1996 (HIPAA). Those regulations require a signed subject authorization informing the subject of the following:

- What protected health information (PHI) will be collected from subjects in this study
- Who will have access to that information and why
- Who will use or disclose that information

The rights of a research subject to revoke their authorization for use of their PHI. (This information is contained within the Mayo IRB Informed Consent Template Section). Study data will be securely stored on a password protected computer that only the research study team will have access to. Any study related paper documents will be stored in a locked cabinet that only the research study team will have access to.

In the event that a subject revokes authorization to collect or use PHI, the investigator, by regulation, retains the ability to use all information collected prior to the revocation of subject authorization. For subjects that have revoked authorization to collect or use PHI, attempts should be made to obtain permission to collect at least vital status (long term survival status that the subject is alive) at the end of their scheduled study period.

9.2 Source Documents

Source data is all information, original records of clinical findings, observations, or other activities in a clinical trial necessary for the reconstruction and evaluation of the trial. Source data are contained in source documents. Examples of these original documents, and data records include: hospital records, clinical and office charts, laboratory notes, memoranda, subjects' diaries or evaluation checklists, pharmacy dispensing records, recorded data from automated instruments, copies or transcriptions certified after verification as being accurate and complete, microfiches, photographic negatives, microfilm or magnetic media, x-rays, subject files, and records kept at the pharmacy, at the laboratories, and at medico-technical departments involved in the clinical trial.

9.3 Case Report Forms

The study case report form (CRF) is the primary data collection instrument for the study. All data requested on the CRF must be recorded. All missing data must be explained. If a space on the CRF is left blank because the procedure was not done or the question was not asked, write "N/D". If the item is not applicable to the individual case, write "N/A". All entries should be printed legibly in black ink. If any entry error has been made, to correct such an error, draw a single straight line through the incorrect entry and enter the correct data above it. All such changes must be initialed and dated. Do not erase or use "white-out" for errors. For clarification of illegible or uncertain entries, print the clarification above the item, then initial and date it. If the reason for the correction is not clear or needs additional explanation, neatly include the details to justify the correction.

Data Security and Confidentiality

All study data will be collected by the research team, reviewed by the PI, and stored in secure, locked files and/or databases in order to protect it from inadvertent loss or improper access. All laboratory specimens, evaluation forms, reports, and other records will be identified by coded number only to maintain subject confidentiality. Information gained from this study that can be linked to the subject's identity will not be released to anyone other than the investigators, the subject and the subject's physician. All the information obtained in connection with these studies will remain confidential as far as possible within state and federal

law. The results of these studies will be published in scientific journals without identifying the subjects by name.

Data Quality Assurance

Source document verification will be performed to ensure that the database accurately reflects data on the CRFs.

Data Clarification Process

